3.1 Primary Objective

1. What is the most effective first-stage treatment for caries prevention, assessed via caries incidence?

3.2 Secondary Objectives

2. What is the most effective sequence of treatments to reduce treatment nonresponse, assessed via caries incidence?
3. What is the optimal dynamic treatment regime given patient attributes, assessed via varies incidence modified by disease severity, sociodemographics, and treatment history?
4. Given alternative strategies, what is the most cost-efficient allocation of resources that can most significantly affect population health, measured by time and cost of care?

4 Study Design and Endpoints

4.1 Description of Study Design

BASICS is a phase-III, single-center, Sequential, Multiple Assignment, Randomized Trial (SMART). It will employ alternative treatment pathways based on initial randomization and subsequent response status, with each pair of pathways defining an adaptive intervention. Four dynamic treatment regimes will be embedded in the SMART (see Study Design Schematic). Study agents and interventions used in BASICS include silver diamine fluoride, glass ionomer dental sealants, silver modified atraumatic restorations, fluoride varnish, and an oral hygiene intervention.

4.2 Study Endpoints

4.2.1 Primary Study Endpoints

Primary study endpoints include the number of new dental caries observed and the person-level prevalence of dental caries, which reflects the number of participants that did not respond to care (nonresponse). These outcomes were selected as they are standard outcomes for school-based caries prevention programs and they directly link to measuring treatment nonresponse.

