Objectives	
 1. What is the most effective first-stage treatment for caries prevention, assessed via caries incidence? 2. What is the most effective sequence of treatments to reduce treatment nonresponse, assessed via caries incidence? 3. What is the optimal dynamic treatment regime given patient attributes, assessed via varies incidence modified by disease severity, sociodemographics, and treatment history? 4. Given alternative strategies, what is the most cost-efficient allocation of resources that can most significantly affect population health, measured by time and cost of care?
Methodology	Sequential, Multiple-Assignment, Randomized Trial (SMART)
Endpoint	The primary study endpoint is treatment nonresponse, defined as presence/absence of caries and the total number of caries observed.
Study Duration	Five years

Participant Duration	2.5 years
Duration of IP administration	Five years
Population	Our targeted enrollment is 1200 children aged 5-12 years. From prior studies, we anticipate an equal sex allocation, and average age of 7.2 years, predominantly from low-income families. The general health status of the population is healthy.
Study Sites	Schools participating in the Schoolyard Smiles SBCP
Number of participants	1200

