Nonresponse will be determined at the second and third post-baseline observational periods by the diagnosis of any dental caries on posterior dentition, including any new caries on previously sound dentition (primary prevention failure) or any teeth diagnosed at baseline with caries that failed to demonstrate arrest (secondary prevention failure). The total number of caries will also be recorded. Responders to either first stage treatment will continue to receive biannual screenings for retention and responsiveness. Non-responders will subsequently proceed to second-stage randomization.

Nonresponders in Trajectory 1 will receive a second-stage randomization to either SDF reapplication plus fluoride varnish receipt of an electronic toothbrush, or an SDF reapplication plus dental sealants. As nonresponse is determined by the diagnosis of new caries, this latter pathway will take the form of delayed silver-modified atraumatic restorative treatment (delayed SMART) [22, 23] on any affected teeth and application of sealants to any remaining sound dentition. Similarly, nonresponders in Trajectory 2 will be randomized to either an augmented treatment of sealant reapplication (including atraumatic restorations) plus fluoride varnish and receipt of an electronic toothbrush or an intensified protocol of SMART on affected dentition. Caries incidence will continue to be evaluated at each remaining planned observation.

Additional design procedures include (1) any patients with sealants that are not retained but no decay is indicated will be considered responsive and the sealant will be reapplied; (2) any patients with atraumatic restorations that are not retained will be considered non-responsive, as it cannot be robustly determined if there is no new decay; (3) any responding participant who transitions to nonresponse after the predetermined nonresponse periods will continue to receive their original first-stage intervention and the total days that elapsed before nonresponse was observed will be recorded; (4) any nonresponding patient who continues to fail to respond will receive reapplication/reinforcement of their second-stage intervention; (5) any new dentition that erupts in either Phase 1 or Phase 2 will receive the corresponding treatment for that phase (e.g., first-stage or second-stage randomized treatment).

7.1.2

Standard of Care Study Procedures

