7.3 Study Schedule

All of the visits described below are part of the research study. Study participants are still part of the school-based caries prevention program at the same time.

7.3.1

Screening

Screening (Day -28 to -1)

- Obtain informed consent of potential participant verified by signature on written informed consent for screening form.
- Review medical history to determine eligibility based on inclusion/exclusion criteria.
- Review dental history to determine eligibility based on inclusion/exclusion criteria.
- Schedule study visits for participants who are eligible and available for the duration of the study.

7.3.2

Enrollment/Baseline

Enrollment/Baseline Visit (Visit 1, Day 0)

- Obtain informed consent of potential participant, if not obtained in Screening period
- Verify inclusion/exclusion criteria.
- Perform comprehensive oral examination
- Administer the study treatment following first-stage randomization (See Figure 1):
 - Either silver diamine fluoride or glass ionomer cement sealants

7.3.3

Intermediate Visits

7.3.3.1 Visit 2

(Day 160-200)

- Record adverse events as reported by participant or observed by investigator.
- Perform comprehensive oral examination
- Record patients responsiveness status
- Proceed with second stage randomization if determined by comprehensive examination to be in treatment nonresponse (See Figure 1)
- Administer relevant treatment as indicated by second stage randomization

7.3.3.2 Visit 3

(Day 340-380)

- Record adverse events as reported by participant or observed by investigator.
- Perform comprehensive oral examination

- Record patients responsiveness status
- Proceed with second stage randomization if determined by comprehensive examination to be in treatment nonresponse (See Figure 1)
- Administer relevant treatment as indicated by second stage randomization

7.3.3.3 Visit 4

(Day 520-560)

- Record adverse events as reported by participant or observed by investigator.
- Perform comprehensive oral examination
- Document clinical outcomes
- Maintain treatment as indicated in Subgroup (Figure 1)

7.3.3.4 Visit 5

(Day 700-740)

- Record adverse events as reported by participant or observed by investigator.
- Perform comprehensive oral examination
- Record patients responsiveness status
- Document clinical outcomes
- Maintain treatment as indicated in Subgroup (Figure 1)

7.3.4

Final Study Visit

Final Study Visit (Visit 6, Day 880-920)

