7.4 Concomitant Medications, Treatments, and Procedures

Concomitant medications are not applicable. However, concomitant treatments and procedures that are observed through oral examinations (e.g., care provided by an external dentist, such as evidence of teeth with fillings that were not observed previously) will be noted in EHRs.

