10.2 Statistical Hypotheses

The null hypothesis is that there is no difference in treatment nonresponse between first stage assignments (SDF compared to dental sealants). The alternative hypothesis is that they are different. The study is a superiority trial. Endpoints will be evaluated at the end of the treatment nonresponse observational window (Study visit 3) and at the completion of subsequent visits (Study visit 4, 5, and 6).

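### Caries prevalence is equated with treatment nonresponse, yet a Visit 2 nonresponder who is re-treated successfully can be caries-free at Visit 3

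*Protocol*

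**What the plan says.** **Endpoint.** Section 4.2.1 lists the count of new caries and the "person-level prevalence of dental caries, which reflects the number of participants that did not respond to care (nonresponse"). The Protocol Summary is more direct: "The primary study endpoint is treatment nonresponse, defined as presence/absence of caries and the total number of caries observed".

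**Operational definition.** Section 7.1.1 works differently: "Nonresponse will be determined at the second and third post-baseline observational periods by the diagnosis of any dental caries on posterior dentition". Qualifying diagnoses are new caries on sound teeth or a baseline lesion that failed to arrest. The same section codes each surface as sound, sealed, restored, decayed or arrested, so a treated lesion is no longer in the decayed category.

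**Treatment inside the window.** For Visit 2, and again for Visit 3, section 7.3.3 instructs: "Proceed with second stage randomization if determined by comprehensive examination to be in treatment nonresponse", followed by "Administer relevant treatment as indicated by second stage randomization". Second-stage treatment of a Visit 2 nonresponder therefore starts about six months before Visit 3.

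**Hypothesis and timing.** The null in section 10.2 is equal nonresponse between the two first-stage assignments. "Endpoints will be evaluated at the end of the treatment nonresponse observational window (Study visit 3"), and again at Visits 4, 5 and 6.

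**Model.** Section 10.4.2 gives presence of caries and presence of nonresponse as two separate binary outcomes. It does not say which of them tests the 10.2 hypothesis.

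**The concern.** Prevalence at a visit and nonresponse over a window coincide only if nothing is treated between the observations. Here treatment is given in between, and only to the children who have already failed. The summary and 4.2.1 say the two are the same quantity; 7.1.1 and 7.3.3 make them different; 10.4.2 lists them separately. An analyst starting from 4.2.1 and the Visit 3 time in 10.2 could score a Visit 2 failure as a success because the second-stage treatment worked.

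At stake is the test of the primary hypothesis. Such an analysis would miss part of the first-stage failures and bring the effect of second-stage care into a comparison described as first-stage nonresponse. The second-stage options differ between the SDF and the sealant trajectories, so the distortion need not be equal in the two arms.

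The window itself is labelled in two ways. With Visit 1 as baseline, the second and third post-baseline periods of 7.1.1 are literally Visits 3 and 4. The Observation and Treatment Schedule, section 7.3.3 and the Schedule of Events place the determination at Visits 2 and 3, and section 10.2 ends the window at Visit 3.

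**Working it through.** **1. One child under each text.** Suppose a child has a new posterior lesion at Visit 2, is re-randomised and treated that day, and at Visit 3 the surface is coded restored or arrested with no other lesion.

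| Text | Status of this child at the close of the window |
|---|---|
| 7.1.1 (diagnosis at either observation) | Nonresponder |
| 4.2.1 and Protocol Summary, read at Visit 3 | No caries, so not a nonresponder |
| 10.4.2 | Nonresponse = yes, caries presence = no |

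The definitions disagree for this child.

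**2. The plan's own figure.** No Visit 3 prevalence is stated. The nearest figure is the 30% nonresponse rate of section 10.5. The subgroup table reproduces it: 420 + 90 + 90 = 600 per trajectory, and (90 + 90)/600 = 30%. That 30% counts children ever classified as nonresponders, which is the 7.1.1 quantity. The N of 122 in 10.5 rests on a standardised effect of 0.5 and does not bear on this point.

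**3. Illustration under equal clearance.** Assumed, not stated in the protocol: cumulative nonresponse NR of 30% vs 22%; a share s = 0.5 found at Visit 2; a fraction c = 0.5 to 0.9 of those children caries-free at Visit 3; no new lesions in cleared children. The range for c is close to the 47% to 90% arrest after one SDF application quoted in section 2.2.2, but that figure is per lesion, not per child. The number per arm is 600 × 0.90 = 540, using the 10% dropout of 10.5.

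Visit 3 prevalence = NR(1 − s) + NR·s(1 − c) = NR(1 − s·c).

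Power = Φ(|p1 − p2| / √{[p1(1 − p1) + p2(1 − p2)]/n} − 1.96), n = 540.

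| Endpoint | Arm 1 | Arm 2 | Difference | Power |
|---|---|---|---|---|
| Ever nonresponder | 30.0% | 22.0% | 8.0 points | 0.853 |
| Visit 3 prevalence, c = 0.5 | 0.30 × 0.75 = 22.5% | 0.22 × 0.75 = 16.5% | 6.0 points | 0.704 |
| Visit 3 prevalence, c = 0.9 | 0.30 × 0.55 = 16.5% | 0.22 × 0.55 = 12.1% | 4.4 points | 0.544 |

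The fraction of nonresponders missed is s·c, so 25% to 45% here. With s from 0.5 to 0.8 and c from 0.47 to 0.90 it is 23% to 72%, or 42 to 130 of the 180 expected in an arm of 600 at 30%.

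**4. Unequal clearance (s = 0.5).**

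- True 30% vs 22%, clearance 90% vs 50%: 0.30 × 0.55 = 16.5% and 0.22 × 0.75 = 16.5%. The difference vanishes.
- True 30% vs 22%, clearance 50% vs 90%: 0.30 × 0.75 = 22.5% and 0.22 × 0.55 = 12.1%. The difference grows to 10.4 points.
- True 30% in both arms, clearance 90% vs 50%: 16.5% vs 22.5%. A false difference of 6 points appears, and by the formula above it would be declared significant about 70% of the time.

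The direction of the bias is not fixed.

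**The case against.** The strongest reply is that the protocol never says the test uses prevalence at Visit 3. Section 4.2.1 names no visit. Section 10.2 speaks of evaluation when the window ends, which fits a status accumulated through it. Section 10.4.2 models nonresponse as its own outcome, and a child classified at Visit 2 stays in subgroup B, C, E or F. On that reading the cumulative endpoint is already there. This stands in part: the point-prevalence analysis is inferred, and the Visit 2 failures are recorded rather than lost from the trial. It does not remove the conflict, because 4.2.1 and the summary still equate the two quantities and nothing says which outcome tests the hypothesis.

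Further limits also stand:

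- Only Visit 2 failures whose re-treatment succeeded would be missed. Children still or newly carious at Visit 3 count, and under 7.1.1 an atraumatic restoration that is not retained is nonresponse by rule.
- The first-stage main effect in 10.5 (A+B+C vs D+E+F) averages over second-stage treatment by construction. Visit 3 prevalence can be a legitimate outcome in that sense; the fault lies in calling it nonresponse.
- The count of new caries, the other listed endpoint, need not lose these failures if it is cumulative.
- How to score surfaces filled by an outside dentist (section 7.4) is a derivation rule commonly left to the SAP, and is not part of this point.

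**Conclusion.** The endpoint is wrong as written. The summary and 4.2.1 identify nonresponse with presence or prevalence of caries, while 7.1.1 and 7.3.3 create children who are nonresponders and yet caries-free at Visit 3. The different labels for the window add to the problem, because they decide which examinations count.

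The size is conditional. If Visit 3 prevalence were used as nonresponse, power would fall from about 85% to between 70% and 54% under the assumed 30% vs 22%, a half share at Visit 2, equal 50% to 90% clearance and 540 per arm. None of the 22%, the half share or the person-level clearance comes from the protocol.

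Three stronger conclusions are tempting but not supported:

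- That the protocol fixes the primary test as Visit 3 prevalence. It leaves this open.
- That the effect is diluted toward the null. This follows only from equal clearance; with different second-stage options per trajectory the bias can shrink, enlarge or create a difference.
- That nonresponse would be understated against the 30% planning value and so upset the sample size. That 30% sizes the second-stage randomisation on ever-classified children; Visit 3 prevalence does not enter it.

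**What to change.** 1. In the Protocol Summary, 4.2.1 and 10.2, define the primary nonresponse endpoint as ever meeting the 7.1.1 definition at any examination up to the close of the window, regardless of later treatment. State in 10.4.2 that this outcome tests the 10.2 hypothesis.
2. Keep visit-specific caries prevalence as a separate outcome, described as averaged over second-stage treatment, and do not call it nonresponse.
3. Reconcile the post-baseline periods named in 7.1.1 with the visits in the Observation and Treatment Schedule, 7.3.3, 10.2 and the Schedule of Events, so that one set of visits forms the window.

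The cost is wording and a derivation rule. Examination findings and response status are already recorded at the visits concerned, so no new data are needed. A cumulative endpoint does need a stated treatment of children who miss one examination in the window, which the imputation already foreseen in 10.4.2 can cover. The change is best made before first treatment, estimated for Fall 2026.

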4.2.2 Secondary Study Endpoints

The secondary study endpoints are costs and cost differences between sequential treatments (arithmetic means). These endpoints were selected as there is significant variation in school caries prevention program design and implementation that is unaccounted for in economic evaluations, highlighting the lack of robustness in economic studies of dental interventions.

4.2.3 Exploratory Endpoints

Not applicable.

5 Study Enrollment and Withdrawal

To facilitate recruitment, enrollment, treatment, and data collection, BASICS will be implemented in an existing school-based caries prevention program that already provides the same treatments proposed in the study. The SBCP program will collect informed consent (for program participation) and school MOUs as part of its natural program operation. Any child participating in the SBCP program will be eligible to participate in the BASICS study. All parents and guardians of program participants will be sent a BASICS study information sheet and separate informed consent document for participation in the study. A minimum of ten schools from the SBCP program will be included in the BASICS study.

5.1 Inclusion Criteria

In order to be eligible to participate in this study, an individual must meet all of the following criteria:

1. Be enrolled in participating schools
2. Be between the ages of 5 and 13 years
3. Provide parental/guardian informed consent
4. Child assent

5.2 Exclusion Criteria

Participants with any of the following criteria will be excluded from participation in this study:

1. ulcerative gingivitis or stomatitis
2. known sensitivity to silver or other heavy-metal ions
3. more than six affected sites
4. those who have had full mouth gingivectomies
5. patients showing abnormal skin sensitization in daily circumstances
6. those who have had pulp capping
7. patients with a known sensitivity to ingredients including colophony (kolophonium) and rosin
8. known allergic reaction to fluoride

These criteria will be confirmed by the study dentist prior to performing the study procedures and by parental attestation in the consent form.

5.3 Vulnerable Subjects

This study primarily involves children.

5.4 Strategies for Recruitment and Retention

All children in eligible grades in participating schools will receive informational sheets along with study consent documents. Study documents (parent information sheet and permission form, child assent) will be given to the participating SBCP, which will then include study documents with the other consent forms used by the SBCP. The SBCP will direct children to take sheets home and give them to the parent or guardian. The recruitment plan does not use any NYULH media services. All recruitment materials (informational sheets) will be submitted for approval by the IRB. Women and minorities will be included (approximately 50% women and 15% minority).

After signature by parents/guardians, the signed consent form will be returned to the school and collected by study investigators. The treating dentist will then sign the parental permission form once it is returned by parents.

Assent from children will be obtained by the treating dentist prior to the study treatment.

5.4.1 Use of DataCore/Epic Information for Recruitment Purposes

This study will not utilize DataCore/EPIC for recruiting purposes.

5.5 Duration of Study Participation

Participants are expected to participate for a minimum of 2.5 years

5.6 Total Number of Participants and Sites

Recruitment will end when approximately 1200 participants are enrolled. It is expected that approximately 3000 participants will be invited to participate in order to produce 1200 evaluable participants.

5.7 Participant Withdrawal or Termination

5.7.1 Reasons for Withdrawal or Termination

Participants are free to withdraw from participation in the study at any time upon request. An investigator may terminate participation in the study if:

- Any clinical adverse event (AE), laboratory abnormality, or other medical condition or situation occurs such that continued participation in the study would not be in the best interest of the participant
- The participant meets an exclusion criterion (either newly developed or not previously recognized) that precludes further study participation

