5.7.2 Handling of Participant Withdrawals or Termination

As a pragmatic trial, it is accepted that enrolled children – who are students at participating schools – may be lost to follow-up (e.g., moved away, enrolled in another school, or other reason). As a result, no attempts will be made to follow-up with withdrawn or terminated participants.

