- Record adverse events as reported by participant or observed by investigator.
- Perform comprehensive oral examination
- Record patients responsiveness status
- Document clinical outcomes
- Provide all participants with any needed care (dental sealants on sound dentition, ART or SMART on any carious posterior dentition, in accordance with Figure 1)

7.3.5

Withdrawal/Early Termination Visit

If the patient is willing, a final comprehensive exam will be provided if a subject withdraws from the study.

7.3.6

Unscheduled Visit

There are no unscheduled visits.

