10.3 Analysis Datasets

Analytic datasets will include intention-to-treat (all randomized participants) and per-protocol (those who completed enough visits sufficiently to ensure the full time for nonresponse has been observed, through third visit)

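### A child who newly exceeds six affected sites can be terminated and is then not followed, so exit can depend on the caries outcome itself

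*Protocol*

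**What the plan says.** Section 5.2 of the Protocol lists eight exclusion criteria. The third is "more than six affected sites"; the term is not defined further.

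Section 5.7.1 is permissive. It opens "An investigator may terminate participation in the study if" and gives as one ground: "The participant meets an exclusion criterion (either newly developed or not previously recognized) that precludes further study participation". No criterion is exempted. Section 5.7.2 explains that children may be lost because they move or change school, and concludes that "no attempts will be made to follow-up with withdrawn or terminated participants". Section 7.3.5 adds that, if the patient is willing, "a final comprehensive exam will be provided if a subject withdraws from the study".

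Section 4.2.1 states: "Primary study endpoints include the number of new dental caries observed and the person-level prevalence of dental caries". On timing, Section 10.2 says: "Endpoints will be evaluated at the end of the treatment nonresponse observational window (Study visit 3) and at the completion of subsequent visits", naming visits 4, 5 and 6.

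Section 7.1.1 deals with treatment failure directly. Nonresponders go to second-stage randomisation, those who go on failing have their second-stage intervention repeated or reinforced, and caries is assessed at each remaining planned visit. Section 10.6.1 states that the clinical investigators cannot be blinded. Section 10.3 defines the intention-to-treat set as everyone randomised, and Section 10.4.2 handles missing data by time-ordered nested conditional imputation.

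**The concern.** A limit on disease burden at entry is ordinary. It becomes a problem when the same limit can be applied after randomisation in a trial whose endpoint is disease burden. Passing the limit is then an extreme form of the endpoint, and termination turns it into missing data at later visits.

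Two features sharpen this. The decision is discretionary and is taken by clinicians who know the assignment, so it could be used differently by arm. And visits 2 and 3 are where nonresponders are re-randomised. A child terminated there may never enter subgroup B, C, E or F, and the second-stage comparisons and embedded regimes would then be evaluated without some of the most severe failures.

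The reason given for not following children, that they have left the school, does not fit a child who is terminated for disease and remains a pupil in the programme.

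**Working it through.** The documents give no figure for exits of this kind. The 10% drop-out allowance in Section 10.5 does not separate causes. The check is therefore mainly a reading of the sections together.

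**1. Is the criterion a measure of the endpoint?** Criterion 3 in Section 5.2 counts affected sites; Section 4.2.1 counts new caries and caries prevalence. They overlap, though not exactly: arrested or baseline lesions may or may not count as affected.

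**2. Does it reach past enrolment?** Yes. Section 5.7.1 covers criteria that develop later, subject to the qualifier that the criterion precludes further participation. The Protocol does not say which criteria do so.

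**3. What happens next?** Section 5.7.2: no follow-up attempts. Section 7.3.5 offers one voluntary examination, worded for a subject who withdraws.

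**4. Does other text disagree?** Yes. Section 7.1.1 keeps the persistently failing child in treatment and under examination. The same child could be handled either way.

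**5. What is lost?** Section 7.3 requires a full examination at every visit, with response status or outcomes recorded. The visit that triggers termination is therefore in the database.

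| Terminated at | Still recorded | Lost |
|---|---|---|
| Visit 2 | visits 1–2 | visits 3–6 (four), possibly second-stage randomisation |
| Visit 3 | visits 1–3 | visits 4–6 (three), possibly second-stage randomisation if not already done |
| Visit 4 | visits 1–4 | visits 5–6 (two) |
| Visit 5 | visits 1–5 | visit 6 (one) |

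A child whose new or unarrested lesions are found at visit 2 or 3 is already recorded as a nonresponder, so first-stage nonresponse through visit 3 is largely protected. The exposure is in the later visits.

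**6. Direction, by illustration only.** Let p be the true caries prevalence at a later visit and s the share of those children already terminated. Among children still seen, prevalence is p(1 − s)/(1 − ps). Take p = 30% in both arms, borrowing the planning nonresponse rate in Section 10.5. The values of s are assumed, with no source in the documents.

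- s = 5%: 0.285/0.985 = 28.9%
- s = 10%: 0.270/0.970 = 27.8%
- s = 20%: 0.240/0.940 = 25.5%
- s = 30%: 0.210/0.910 = 23.1%

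With no true difference, 5% against 10% gives an apparent gap of 1.1 points, 5% against 20% gives 3.4, and 10% against 30% gives 4.8, each in favour of the arm that lost more severe failures. With equal shares the effect is dilution: taking the ends of the 24% to 36% range in Section 2.1 as the two arms, s = 30% gives 0.168/0.928 = 18.1% and 0.252/0.892 = 28.3%, so 12.0 points become 10.1. These figures are before imputation and show direction, not expected size.

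**The case against.** The strongest reply is that the trial's own pathway keeps failures in. Section 7.1.1 is specific to nonresponse, while Section 5.7.1 is general and permissive, and nothing says that exceeding six sites precludes participation. This stands as far as it goes: a reader might infer that the worst failures must leave, and the text does not say so. It leaves two sections that allow opposite handling of the same child.

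Second, exit triggered by a recorded count depends on observed data, which conditional imputation is meant to use. This also has force. A reader might infer that the triggering lesions are lost or that an intention-to-treat analysis is unachievable; neither follows. But imputation needs comparable children with later data. If few children past six sites remain, it must extrapolate, and if unmasked clinicians terminate on grounds not in the record, the recorded history does not fully explain the exit.

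Third, Section 7.3.5 might be read as contradicting Section 5.7.2. One voluntary examination at exit is compatible with no attempts afterwards. The two need aligning, but they do not flatly conflict, and one examination does not replace visits through visit 6.

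Fourth, pulp capping, another Section 5.2 criterion, might be taken as a second caries outcome. It is neither an endpoint nor a study procedure, so the point rests on criterion 3 alone. Nor does the Protocol say that programme records of terminated children will be discarded; it only commits to no follow-up.

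**Conclusion.** The point holds in limited form. Sections 5.2, 5.7.1 and 5.7.2 together permit exit that depends on the endpoint, at the discretion of unmasked investigators, and this conflicts with Section 7.1.1. What is at risk is data after the triggering examination, including possible loss of second-stage randomisation at visits 2 and 3.

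The size is not derivable: it depends on how many children pass six sites, what counts as an affected site, and how often investigators use the clause. The illustrative gaps of 1.1 to 4.8 points rest on assumed shares and on no imputation, and should not be quoted as estimates. If exits are unequal, later-visit counts and prevalence are biased towards the arm that loses more severe failures. This should be fixed; the documents do not show that it invalidates the primary comparison.

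**What to change.** Reconcile Sections 5.2, 5.7.1, 5.7.2, 7.1.1 and 7.3.5 so that they say consistently whether the disease-count criterion applies after randomisation, and define an affected site. Which way that is settled, and whether an individual child stays on study treatment, is a clinical decision for the investigators.

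Whatever they decide, separate the end of study treatment from the end of outcome assessment. In Section 5.7.2, replace the no-follow-up sentence with wording to this effect: children taken off study treatment who have not withdrawn consent and who remain in the school programme continue to contribute their programme examinations, and are analysed under their assigned arm in the intention-to-treat set. Align Section 7.3.5 with it.

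The cost is a short amendment and minor data handling, with a check that the parental permission form covers continued use of programme examinations. The school programme already performs these examinations in the same record system, so no study-specific visits need be added. It is best done before the first treatments, estimated for Fall 2026, because the analysis cannot restore examinations that were never collected.
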